**Randomization:** Participants will be randomized to the ICS prescription arm or the routine asthma care arm. We will use block randomization to balance the number of participants in each arm, and varied block sizes (4 – 8) because of incomplete blinding of assignments. The allocation ratio between intervention and control arms will be 1:1. Random treatment assignments in each block will be generated in advance using a computer algorithm. Assignments will be placed in sealed, opaque, consecutively numbered envelopes by a person not involved in the study. When a participant is enrolled, the RA will take the next envelope, record the envelope study ID for that participant, and open the envelope to determine the assignment.

**ICS Prescription Arm Protocol:** Participants in the ICS prescription arm will follow the treatment plan, discharge instructions, and follow up recommendations provided by the treating clinicians while they are in the ED. During discharge, the study nurse will provide the asthma discharge instructions (see attached instructions) to the family and inform them that the child has met criteria for prescription of an ICS to help control the asthma. The families preferred pharmacy will be determined and a prescription for the first-line ICS covered by the participant's insurance will be called in within 24 hours by the study PI or co-Investigator (both licensed clinicians). Dosing will follow the recommendations outlined in the NHLBI asthma guidelines for low dose ICS in this age group for the respective medication.(19) In addition to the standard instructions, the nurse will give specific instructions for ICS use including how to administer medication, use of

spacer devices to be used with the MDI, recommendations for daily use, possible side effects of medication use, and distinction between controller and quick-relief rescue medications. Parents will be informed that they should follow up with their primary care provider to discuss the length of ICS use.

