Outcome data collected will include unscheduled doctor's office visits, ED visits, hospitalizations, or oral steroid courses for asthma in the 6 months following enrollment. Unscheduled doctor's visits will be corroborated by contacting the child's primary doctor and obtaining a visit history (using the Release of Information form signed during consent). Visits in the week following enrollment will not be included as they will be considered part of the initial exacerbation. To corroborate oral steroid courses, we will contact the participant's pharmacy, using the Release of Information signed during consent.

Another outcome variable collected using a script during the telephone call will be the quality of life, using the ITG-CASF. The ITG-CASF has been validated in the ED setting for children 2 to 17 years old (34), is reliable (Cronbach's  $\alpha = 0.70$ ), can be administered by telephone (34), requires only 10 questions, and has been used in studies with similar follow up timeframes.(10) Each item is rated on a 5-point scale. Each response is scaled as a percentage of the maximum response, and the total score is the maximum percentage based on the number of questions answered. The scores range from 0 – 100, with higher scores reflecting better quality of life. The change in ITG-CASF scores for children with improved overall clinical status are 10 points higher than when children have not improved.(34)

**Data Analysis Plan:** Participants will be analyzed in the group to which they were randomized using an intention-to-treat approach. We hypothesize that children in the intervention arm will have less unscheduled health care use at 6 month follow up, and increased quality of life compared to children receiving routine asthma care. We will use chi-square testing for the health care use variable, and Student's t-test for the continuous quality of life variable.

**Power Analysis:** Sample size was calculated to power hypothesis testing for dichotomous health care use outcomes as they require the largest sample size. Using preliminary data to estimate baseline health care use in our study population,(35) we calculated the sample size needed to detect a difference in the proportion of children with unscheduled health care use in the intervention arm

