( $p_1=0.35$ ) compared to the routine asthma care arm ( $p_0=0.6$ ), with 80% power to detect a statistically significant difference at an alpha of 0.05. Assuming 20% of participants will not be reached for follow up, and who will not have outcome data available when electronic medical records are audited, we will recruit 143 participants to achieve our sample size of 114.

**Data Safety and Monitoring Plan (DSMP):** The goals of the DSMP are three-fold. First, it is to ensure that there is no statistical difference in adverse events between the two study arms. Second, all serious adverse events will be reviewed by the members to provide direction on study continuation. Serious adverse events are considered very unlikely with this study protocol, since the two treatment conditions are both commonly utilized treatments in clinical practice. The third goal is to ensure that the intervention arm is not performing significantly better than the routine asthma care arm, as if this was identified early in the study, it would be unethical to withhold the intervention from the control arm.

Prior to beginning enrollment, we will have a conference call at which time the DSMP will be reviewed by the study PI and 2 Emergency Medicine attendings not affiliated with the study. The first DSMP data review will occur 6 months after the first participant has their 6 month data collection. Therefore this meeting will likely occur 12 months after study enrollment begins. Reviews will occur every 6 months thereafter.

The following outcome data will be provided to the DSMB along with the randomization assignments:

- Unscheduled medical visits to primary doctor's office for asthma
- ED visits for asthma
- Hospitalization for asthma
- Oral steroid courses for asthma
- Quality-of-life scores from the ITG-CASF
- Adverse events reported by parents at 6 month follow-up phone call
- Adverse events reported by study personnel
- Serious adverse events reported by study personnel\*

\* Any serious adverse events will be reported within 24 hours of occurrence to the IRB and DSMB. Study enrollment will be suspended until the DSMB and IRB have reviewed the event and made recommendations to the study PI.

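### The stated 80% power does not follow from the printed inputs: with 114 evaluable children, a two-sided chi-square test of 0.60 vs 0.35 has about 77% power

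*Combined protocol and SAP*

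**What the plan says.** The Power Analysis section sizes the trial on the dichotomous health care use outcome. The control proportion is derived as follows: "Using preliminary data to estimate baseline health care use in our study population". It is printed as 0.6, and the intervention proportion as 0.35. The design is to detect this difference "with 80% power to detect a statistically significant difference at an alpha of 0.05". For attrition the plan writes "Assuming 20% of participants will not be reached for follow up", and it ends with "we will recruit 143 participants to achieve our sample size of 114".

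Two other sections of the protocol fix the remaining inputs. The Data Analysis Plan names the test: "We will use chi-square testing for the health care use variable". The Randomization section says "The allocation ratio between intervention and control arms will be 1:1".

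Neither the Power Analysis nor the Data Analysis Plan gives the sample size formula, the sidedness of the test, or whether a continuity correction is used. The hypothesis is worded directionally ("We hypothesize that children in the intervention arm will have less unscheduled health care use at 6 month follow up"), but no one-sided test is named.

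**The concern.** A power statement should be reproducible from the numbers printed beside it. Here the two proportions, alpha, the test, the allocation ratio and the evaluable number are all given, yet the usual calculation for a two-sided chi-square test does not return 114 for 80% power.

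At stake is how much assurance the design gives against missing a real effect. If the printed inputs are the true planning inputs, the type II error at the design effect is about 23% rather than 20%. The result is also sensitive to a control proportion that is printed to one decimal only.

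**Working it through.** **Inputs.** p0 = 0.60, p1 = 0.35, alpha 0.05, target power 80%, 114 evaluable, 143 recruited and 20% loss (Power Analysis); chi-square test (Data Analysis Plan); 1:1 allocation, hence 57 per arm (Randomization). Assumed because not stated: two-sided, no continuity correction.

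**Attrition step.** 114 / (1 − 0.20) = 142.5, rounded up to 143. This reproduces.

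**Sample size, pooled formula.** This is the formula that corresponds to the uncorrected chi-square test. With p̄ = (0.60 + 0.35)/2 = 0.475:

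n per arm = [1.96·√(2·0.475·0.525) + 0.8416·√(0.60·0.40 + 0.35·0.65)]² / 0.25²
= [1.96·0.7062 + 0.8416·0.6837]² / 0.0625
= 61.44, so 62 per arm or 124 in total. The plan has 114.

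**Power at 57 per arm, same formula.**

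Φ{[0.25·√57 − 1.96·0.7062] / 0.6837} = Φ(0.736) = 76.9%.

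**Exact check.** Enumerating all binomial outcomes and applying the Pearson chi-square test to each uses no sample size formula. Power for 0.60 vs 0.35 is then:

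| n per arm | 57 | 58 | 59 | 60 | 61 | 62 |
|---|---|---|---|---|---|---|
| exact power | 76.8% | 78.0% | 79.2% | 80.3% | 81.4% | 82.4% |

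It stays above 80% at 63 to 65 per arm, so 120 evaluable children suffice by this route. Recruiting 143 would yield 120 if loss were 1 − 120/143 = 16.1%, and 124 if it were 1 − 124/143 = 13.3%, against the planned 20%.

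**Other methods at the printed inputs.**

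| Method | Total N for 80% | Power at 57 per arm |
|---|---|---|
| Two-sided, unpooled variance | 118 | 78.8% |
| Two-sided, arcsine | 124 | 77.1% |
| Two-sided, continuity-corrected | 140 | 70.6% (exact 70.5%) |
| One-sided, uncorrected | 98 | 85.6% |
| One-sided, continuity-corrected | 112 | 80.7% |

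None returns 114. The one-sided continuity-corrected calculation comes closest (55.99 per arm, so 56).

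**Rounding of the control proportion.** With p1 = 0.35, two-sided, 57 per arm:

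| p0 | 0.59 | 0.60 | 0.605 | 0.61 |
|---|---|---|---|---|
| formula | 73.4% | 76.9% | 78.6% | 80.2% |
| exact | 73.3% | 76.8% | 78.4% | 80.0% |

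The pooled formula gives 56.8 per arm at p0 = 0.61. It rounds up to exactly 57 for p0 from 0.6095 to just under 0.6118, values that would print as 0.6 to one decimal. Holding p0 at 0.60, power at 57 per arm reaches 80% at p1 = 0.34 (80.2% formula, 80.1% exact).

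**The case against.** The best counter-argument is that the plan is under-specified rather than wrong. With no sidedness, formula or correction stated, 114 may be the correct output of a method that was not written down. A one-sided continuity-corrected calculation gives 112. The unpooled formula gives 78.8% power at 57 per arm, and with p0 = 0.604 it gives 56.8, so 57. Rounding in both proportions also works: under the pooled formula, 0.605 vs 0.345 needs 56.7 per arm. The control proportion comes from preliminary data that the documents do not reproduce. Moreover, 3 points is small beside the uncertainty in that proportion, and a null result will be read mainly from the observed difference and its confidence interval.

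Much of this stands. The source of the mismatch is unknown, rounding is a plausible cause, and the practical effect is limited. It does not rescue the printed statement, though. Each route needs a feature or an input that the plan does not print, and none gives 114 at exactly 0.60 vs 0.35. The unpooled formula does not describe the Pearson test, whose exact power is 76.8%. If a continuity correction were meant for a two-sided test, power would be lower still, at about 70.5%. The uncorrected two-sided reading used here is therefore the more favourable of the two. The confidence interval will indeed carry the interpretation of a null result, but that is no reason to leave the design power misstated.

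**Conclusion.** The power statement is not correct as printed. For 0.60 vs 0.35 with 57 evaluable children per arm, a two-sided uncorrected chi-square test at 0.05 has about 77% power, roughly 3 points below the stated 80%. Reaching 80% would take 6 to 10 more evaluable children (120 exact, 124 by formula). The inflation from 114 to 143 is right.

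This rests on three assumptions: a two-sided test, which is the ordinary reading of a chi-square test at 0.05; no continuity correction; and planning proportions equal to the printed ones. If the planning control proportion was about 0.61, then 114 is right and only the printed 0.6 needs correcting. The point should be fixed, but it does not threaten the design.

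**What to change.** Keep 143 recruited and 114 evaluable. Retrieve the calculation behind 114, then print one of two statements in the Power Analysis.

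1. If the planning control proportion was 0.60: *With 57 evaluable children per arm, a two-sided Pearson chi-square test without continuity correction at alpha 0.05 has about 77% power for 0.60 vs 0.35 (80% for 0.60 vs 0.34).*
2. If the unrounded planning value was about 0.61: print p0 = 0.61, for which 57 per arm gives 80% power.

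If the calculation cannot be found, use the first statement, since it is the one that follows from the inputs now in the protocol. In either case, give the sample size formula and state in the Data Analysis Plan that the chi-square test is two-sided without continuity correction, so that the test and the power statement describe the same analysis.

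The cost is wording only, with no extra participants. Under the first statement the declared power becomes slightly less favourable.

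### Six-monthly reviews look for a significant ICS benefit with no interim boundary; testing at 0.05 each time would push type I error above 5%

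*Combined protocol and SAP*

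**What the plan says.** The Data Safety and Monitoring Plan (DSMP) lists three goals, and the last concerns efficacy: "The third goal is to ensure that the intervention arm is not performing significantly better than the routine asthma care arm". The reason given is that, if a benefit were seen early, "it would be unethical to withhold the intervention from the control arm".

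The first data review follows six months after the first child's six-month data collection: "Therefore this meeting will likely occur 12 months after study enrollment begins". After that, "Reviews will occur every 6 months thereafter". The reviewers see results by arm: "The following outcome data will be provided to the DSMB along with the randomization assignments". The list that follows includes office visits, ED visits, hospitalizations, oral steroid courses and quality-of-life scores.

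The only significance level is in the Power Analysis, where the sample size is set "with 80% power to detect a statistically significant difference at an alpha of 0.05"; whether it is one- or two-sided is not stated. The Data Analysis Plan names ordinary tests with no sequential adjustment: "We will use chi-square testing for the health care use variable", and a t-test for quality of life.

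**The concern.** The DSMP sets a trigger (a significant advantage for ICS) and implies a consequence (control children should no longer go without it). It does not say what level counts as significant at a review, which of the listed outcomes decides, how many reviews there may be, or whether the final test is adjusted for them. Reviewers who look to the document for a threshold will find only 0.05.

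Two things are at stake. A benefit declared at a review, or at the end after several reviews, would not carry the 5% error rate that the plan states. And a trial stopped because the difference happened to be large at that moment reports too large a difference, especially when the first review may rest on a few dozen children or fewer.

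**Working it through.** **Inputs.** From the Power Analysis: 0.60 versus 0.35, alpha 0.05, 80% power, 114 evaluable, 143 recruited with 20% loss. From Randomization: 1:1 allocation in blocks of 4 to 8. From the Data Analysis Plan: chi-square test. From the DSMP: reviews at about months 12, 18, 24 and so on. Outcomes mature six months after enrolment.

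**Assumptions.** Even accrual; one outcome; two-sided 0.05 at each look; a review can stop the trial only for benefit; the final test is two-sided. Enrolment length E is not stated, so 12 to 36 months is shown.

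**The plan's own figures.** 114 / (1 − 0.20) = 142.5, so 143 as stated. Two-sided power with 57 per arm and pooled variance under the null:

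- null SE = √(2 × 0.475 × 0.525 / 57) = 0.0935
- alternative SE = √((0.35 × 0.65 + 0.60 × 0.40) / 57) = 0.0906
- power = Φ((0.25 − 1.96 × 0.0935) / 0.0906) = 76.9%

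The unpooled formula gives 78.8%. The shortfall from 80% is a separate matter; about 77% is the benchmark for a single final test below.

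**Number of reviews.** At month m, 114 × (m − 6) / E children have outcomes, and the final analysis is at month E + 6. With E = 24, for example, reviews fall at months 12, 18 and 24 before a final analysis at month 30, and the first has 114 × 6 / 24 = 28.5 children. With E of 6 or less, all outcomes are in by the first review and nothing is inflated.

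**Type I error.** The looks are equally spaced, so the correlation of the test statistics at looks j < k is √(j/k). With one interim review:

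- falsely favouring ICS = 0.025 + 0.025 − P(both looks exceed 1.96) = 0.050 − 0.0084 = 0.0416
- total = 0.0416 + 0.025 (final test favouring routine care) = 0.0666; simulation gave 0.0665

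The other rows come from two million simulated runs each. The last two columns repeat the exercise with 300,000 chi-square trials per row, a true rate of 0.60 in both arms and random blocks of 4, 6 or 8.

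| Enrolment (months) | Interim reviews | Children at first review | Total error | Falsely favouring ICS | Total, chi-square | Favouring ICS, chi-square |
|---|---|---|---|---|---|---|
| 12 | 1 | 57 | 6.7% | 4.2% | 6.9% | 4.4% |
| 18 | 2 | 38 | 7.9% | 5.4% | 7.9% | 5.5% |
| 24 | 3 | 28 | 8.8% | 6.3% | 9.0% | 6.6% |
| 36 | 5 | 19 | 10.2% | 7.7% | 10.9% | 8.4% |

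The reference values are 5% and 2.5%. The gaps of up to 0.7 point reflect small discrete counts at early reviews. If reviews could stop the trial in either direction, total error would be 8.3%, 10.7%, 12.6% and 14.2% for one, two, three and four interim reviews. If 0.05 was meant one-sided, the chance of falsely favouring ICS would rise from 5% to 8.0%, 10.1%, 11.7% or 14.1% over the four rows.

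**Under the planned effect (0.60 versus 0.35).** The mean difference is over all trials, stopped or not; the true value is 25 points.

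| Enrolment (months) | Power, 0.05 looks | Power, p<0.001 looks | Early stops, 0.05 | Early stops, p<0.001 | Mean difference, 0.05 | Mean difference, p<0.001 |
|---|---|---|---|---|---|---|
| 12 | 80.0% | 77% | 52% | 9% | 27.6 | 26.0 |
| 18 | 80.7% | 77% | 63% | 13% | 29.1 | 26.2 |
| 24 | 81.8% | 77% | 70% | 18% | 30.4 | 26.8 |
| 36 | 83.4% | 77% | 77% | 23% | 32.6 | 27.2 |

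**With p<0.001 at reviews and 0.05 at the end,** chi-square total error is 4.9%, 4.8%, 4.9% and 4.9%.

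**The case against.** The strongest reply is that the inflation is hypothetical. The DSMP prescribes no interim test, level or stopping action. Its efficacy goal is worded as loosely as its goal about adverse events, and the pre-enrolment call on the DSMP could settle a boundary. That is fair, and it is why the figures are conditional on 0.05 being used and acted on. But nothing says that the call will set a boundary, and the ethical argument in the DSMP presses towards acting on nominal significance.

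The size is also not anchored: the enrolment range and benefit-only stopping are assumptions, and another choice moves the numbers. This stands as a limit on precision. The direction does not depend on it, because every scenario with an interim look at 0.05 exceeds 5%.

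Two smaller points also stand. The one-sided series fits poorly with a chi-square test, which is non-directional, so it is secondary. The early-stop percentages are sensitive to small shifts: at the first review under 12-month enrolment, 52% and 9% apply to arms of 29 and 28, but 28 per arm gives 45% and 6%. Read them as rough sizes.

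Finally, a strict boundary delays action on a real benefit, which is what the DSMP wants to avoid. That is a true cost, and the sponsor should choose it knowingly.

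**Conclusion.** The concern holds. The plan makes early detection of a significant benefit a monitoring goal and supplies the data for it by arm, but leaves the rule unwritten. If its only stated level is used at each review, total type I error is about 6.7% to 10.2% rather than 5%, and the chance of falsely favouring ICS is about 4.2% to 7.7% rather than 2.5%. The average reported difference becomes about 28 to 33 points when the truth is 25.

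These figures assume 12 to 36 months of even enrolment, 114 evaluable children, one outcome and stopping only for benefit. Several outcomes are supplied and none is named as decisive; choosing among them could add error not counted here. The omission is certain; its numerical effect depends on these assumptions. It should be fixed, because it touches the main efficacy claim and the remedy is simple.

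**What to change.** Add three sentences to the DSMP:

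> At each review, benefit is judged only on the proportion of children with unscheduled health care use, the outcome used in the power analysis. Stopping for benefit is considered only at two-sided p<0.001 (Haybittle-Peto). The final test stays at two-sided 0.05.

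Another boundary fixed in advance would also serve, but an O'Brien-Fleming boundary needs its own slightly lower final level: about 0.048, 0.045 or 0.043 for two, three or four analyses in total.

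The cost is text only, with no extra participants. Power stays at the 77% of a single final test. That is about 3 to 7 points below unadjusted looks at 0.05, which gain their power only by spending extra type I error. The real price is fewer early stops under the planned effect: roughly a tenth to a quarter of trials, instead of half to three quarters.

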One week after study enrollment, the pharmacy to which the prescription was called will be contacted to determine any prescriptions for asthma medications that were filled. Delivery of a doser CT device, which is used to assess medication adherence, will occur approximately one week after study enrollment. This device will be coupled with the ICS MDI (if one was obtained from the pharmacy) or with an albuterol MDI (if no ICS was filled). Families will be called two weeks after the ED visit to determine if there are any issues with device use. To ensure proper communication, a checking-in mailer will be sent out two weeks post-enrollment. This mailer will serve as a reminder to contact staff if participants encounter any issues with the doser CT device or if their contact information has changed. A home visit will be scheduled at one month to arrange for retrieval of the doser CT device. An "Unable to Contact Mailer" will be sent out to participants if staff are unable to contact them after several attempts.

**Routine Asthma Care Arm Protocol:** Participants in the routine asthma care arm will follow the treatment plan developed by the treating clinicians as part of routine care. The study nurses will provide the same asthma discharge instructions (see attached instructions), except for those instructions specific to ICS use.

One week after study enrollment, the child's pharmacy will be contacted to determine any prescriptions for asthma medications that were filled. Delivery of a doser CT device, which is used to assess medication adherence, will occur approximately one week after study enrollment. Unlike in the ICS Prescription Arm, the doser CT device for children in the control arm will be used with their albuterol MDI. Although this data will not be used for analysis, it makes the control arm intervention similar to the intervention arm from the perspective of the study participants. Families will be called after two weeks to determine if there are any issues with device use. To ensure proper communication, a checking-in mailer will be sent out two weeks post-enrollment. This mailer will serve as a reminder to contact staff if participants encounter any issues with the doser CT device or if their contact information has changed. A home visit will be scheduled at one month to arrange for retrieval of the doser CT device. An "Unable to Contact Mailer" will be sent out to participants if staff are unable to contact them after several attempts.

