### **Summary of Intervention and Control Protocol**

Timing after enrollment	Study Procedure	Purpose	Intervention Arm	Control Arm
--	------------------------	----------------	-----------------------------	------------------------

Just prior to ED discharge	Study nurse performs discharge instructions; ICS prescription arm provides preferred pharmacy info	To provide education to both arms (ICS specific for ICS Prescription Arm)	X	X
Within 24 hours	Study clinician (PI) calls preferred pharmacy	To arrange ICS prescription	X	
Within 7 days	Researcher contacts pharmacy	To determine which participants filled an ICS prescription	X	X
One week	Research coordinator or RA arranges for home visit to deliver doser CT device*	To monitor medication adherence	X	X**
Two weeks	RA calls families who received Doser CT devices. A two week checking-in mailer is sent out.	To discuss any problems with the Doser CT device and changes in contact information.	X	X
One month	RA arranges home visit to retrieve Doser CT devices*	Retrieve CT Doser device	X	X
One, Two and four months	RA calls family	To reduce attrition and keep family excited about study	X	X
Six months***	Blinded researcher follow-up phone call	Outcome data collection	X	X

\* Participants will be mailed \$20 compensation for their effort upon completing the 6 month follow-up.

\*\* In Control Arm, Doser CT device will be used with albuterol MDI as sham intervention.

\*\*\* If follow-up phone call is unsuccessful, researcher will attempt home visits to collect outcome data.

**6 Month Follow-up Phone Call and Outcome Variables:** Six months after study enrollment, all participants will be contacted by telephone to collect outcome data. The researcher making the follow up phone calls will be blinded to the study arm of the participants. Telephone calls to participants will continue until follow up is complete, or further participation is refused. Informed consent at the time of enrollment will include permission to perform home-visits if telephone contact is unsuccessful. Participants will be mailed \$20 compensation for their effort upon completing the 6 month follow-up.

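### Only ICS-arm parents are taught side effects at discharge, and no common adverse event question is described, so parent-reported events could differ by arm when true rates do not

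*Combined protocol and SAP*

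**What the plan says.** **Teaching at discharge.** Under ICS Prescription Arm Protocol, the extra teaching is introduced with "In addition to the standard instructions, the nurse will give specific instructions for ICS use", and its listed content includes "possible side effects of medication use". Under Routine Asthma Care Arm Protocol, control families get the same discharge instructions "except for those instructions specific to ICS use". The Summary of Intervention and Control Protocol table shows the same split.

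**Use of adverse event data.** The Data Safety and Monitoring Plan (DSMP) states its opening goal as "First, it is to ensure that there is no statistical difference in adverse events between the two study arms". Its list of data for the DSMB, supplied with the randomization assignments, includes "Adverse events reported by parents at 6 month follow-up phone call". It also includes "Adverse events reported by study personnel", and serious adverse events from the same source.

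**How the 6-month call is described.** The caller is blinded to arm. The section on the 6-month call and outcome variables mentions a script for the ITG-CASF quality-of-life score. It describes outside corroboration for unscheduled doctor's visits and for oral steroid courses. It gives no question wording, checklist, recall period or corroboration for adverse events.

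**The concern.** One group of parents has been told what to look out for and to link to a medicine. The other has not been told this at discharge. Both groups are then asked for adverse events up to six months later, by a method that the plan does not describe, and the answers are compared by arm. If taught parents notice, remember or mention more, the arms will differ in reported events without differing in true events.

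Blinding the caller does not deal with this, because the possible bias lies in what parents bring to the call. ICS-arm parents are told that their child met the criteria for an ICS, and the Randomization section itself acknowledges that blinding is incomplete.

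At stake is how the DSMB reads the parent-reported events. It could take a reporting artefact for a safety signal, or dismiss a real excess as an artefact. The plan gives it little with which to tell the two apart.

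**Working it through.** The plan gives no adverse event rate, reporting rate, margin or test, so there is no safety figure to reproduce. The calculation below illustrates how far unequal reporting could move the comparison. It does not estimate what will happen.

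**Inputs from the protocol**
- Evaluable sample 114 (Power Analysis), from 143 recruited with 20% loss: 143 × 0.8 = 114.4.
- Allocation 1:1 (Randomization), so 114 / 2 = 57 per arm.
- Alpha 0.05 (Power Analysis), taken here as two-sided.

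**Assumptions, none of them documented**
- The true proportion of children with an event is the same in both arms: 5%, 10%, 20% or 30%.
- ICS-arm parents report 80% of events. Control parents report 70%, 60%, 50% or 40%.
- The test is an uncorrected Pearson chi-square.

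**Formulas**
- Reported rate in an arm = true rate × fraction reported. For example, 0.20 × 0.80 = 0.16 and 0.20 × 0.40 = 0.08.
- With X and Y children reported in the ICS and control arms, n = 57 and p̄ = (X + Y)/(2n), the statistic is Z = (X/n − Y/n) / √(2p̄(1 − p̄)/n).
- Chance of a false significant ICS-arm excess = the sum of the two binomial probabilities over all pairs (X, Y) with Z > 1.96.

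**Results at 57 per arm**

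| True rate, both arms | Fraction reported, ICS vs control | Reported rate, ICS vs control | False significant ICS-arm excess |
|---|---|---|---|
| 5% | 80% vs 60% | 4% vs 3% | 3.7% |
| 5% | 80% vs 40% | 4% vs 2% | 6.4% |
| 10% | 80% vs 70% | 8% vs 7% | 3.8% |
| 10% | 80% vs 40% | 8% vs 4% | 13.1% |
| 20% | 70% vs 70% | 14% vs 14% | 2.5% |
| 20% | 80% vs 70% | 16% vs 14% | 4.8% |
| 20% | 80% vs 60% | 16% vs 12% | 8.8% |
| 20% | 80% vs 50% | 16% vs 10% | 15.4% |
| 20% | 80% vs 40% | 16% vs 8% | 25.7% |
| 30% | 80% vs 60% | 24% vs 18% | 12.3% |
| 30% | 80% vs 40% | 24% vs 12% | 39.5% |

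In every row with unequal reporting, the chance of a false control-arm excess falls below 2.5%.

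**Sensitivity**
- *Fewer children.* DSMB reviews take place during the trial. With an assumed 30 per arm, 16% vs 8% gives 16.3% and 16% vs 12% gives 6.7%. With 20 per arm they give 10.7% and 5.2%. These are single looks; repeated looks would add to the cumulative chance.
- *Another test.* Fisher's exact test at 57 per arm gives 16.9% for 16% vs 8% and 5.1% for 16% vs 12%.

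**The case against.** The strongest reply is that the documents show unequal teaching, not unequal reporting. Side effects are one item in a single discharge conversation, and the report comes six months later to a blinded caller. That stands: reporting could differ by arm, but nothing shows that it will.

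A reader might infer that control parents know nothing of ICS side effects. The documents do not support this. Consent comes before randomization, and neither the consent pages nor the attached discharge instructions are available here. Only the difference in teaching at discharge can be confirmed.

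A reader might also infer that the whole safety comparison fails to measure what it claims. That goes too far. Adverse events and serious adverse events reported by study personnel also reach the DSMB and need not share the parent-report problem, although how personnel collect them is not described.

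The consequences are limited as well. The adverse event comparison is a monitoring goal and does not appear in the Data Analysis Plan. No stopping rule is tied to non-serious events; the only automatic pause is for serious ones. The DSMB sees the assignments and can allow for reporting differences.

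Finally, teaching side effects to families given a medicine is not a fault, and the call script is not shown, so a common question may exist. Both points are fair. What remains is that the plan makes this comparison its first monitoring goal and describes no common way of asking.

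**Conclusion.** The concern holds as a possible ascertainment bias in the parent-reported part of the adverse event data. Its most plausible direction is toward an ICS-arm excess. That direction is inferred from the unequal teaching, and an observed excess could equally be real.

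The size is unknown. At 57 per arm, for true rates of 5% to 20%, the illustrative chance of a false significant excess runs from about 4% through 9% to 26%, against about 2.5% with equal reporting. A higher true rate would raise it. A single interim look with fewer children, or Fisher's exact test, would lower it. It would be wrong to quote 26% as this trial's false-alarm rate, because it rests wholly on assumed reporting of 80% vs 40% and a 20% true rate at full sample size.

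The primary health care use outcome is not affected. The change is worth making because it is cheap and the comparison is the first stated DSMP goal.

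**What to change.** Keep the side-effect teaching as it is. Add the following to the description of the 6-month call and to the DSMP:

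1. After the health care use and ITG-CASF questions, the blinded caller asks every parent in both arms the same yes/no symptom list. The wording is neutral, with no mention of ICS or of cause, and covers a fixed recall period. Placing it last keeps it from colouring the efficacy answers.
2. For each symptom reported, the caller asks whether it led to medical contact.
3. The parent-reported adverse event comparison sent to the DSMB is based on this list.
4. Volunteered, medically attended and personnel-reported events are shown separately by arm. Medically attended events are likely to be the parent-reported version least affected by the teaching.

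The cost is a short script and a few extra minutes on a call already planned. Treatment, sample size and endpoints do not change. The effect of parents knowing the arm is reduced but not removed, and the DSMB should be told so.
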